Patients who discontinue from study drug during the 6-month Primary Analysis Period (defined as a discontinuation that occurs after the first dose of study drug administration on Day 1 during the 6-month Primary Analysis Period) will be encouraged to remain on the study and complete all assessments (including 24-hour urine collections) through Month 6, with early termination (ET) assessments at Month 9, and safety follow-up per the safety follow-up schedule (Table 1). Patients who do not remain on the study through Month 6 will be asked to return for their next scheduled visit to complete ET assessments and complete safety follow-up per the safety follow-up schedule (Table 1).

Patients who discontinue study drug after Month 6 will be asked to return for their next scheduled visit to complete ET assessments and complete a safety follow-up visit per the safety follow-up schedule (see Table 1).

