### **5.2.2.** Dose and Administration

Patients will be administered SC injections of lumasiran (284 mg or 567 mg) and/or placebo at the same volume, as described below, on Day 1, Month 3, and Month 9.

Lumasiran 567 mg	Lumasiran 284 mg	Placebo
1.5 mL lumasiran	1.5 mL lumasiran	1.5 mL placebo
1.5 mL lumasiran	1.5 mL placebo	1.5 mL placebo

Study drug injections will be administered under the supervision of the Investigator or healthcare professional. To maintain the blind, syringes are to be masked prior to the removal of study drug from vials. A full description of the blinding procedure is included in the Pharmacy Manual. The injection site may be marked and mapped for later observation. Injections may be administered in the abdomen, thigh, or the side or back of the upper arms. If a local reaction around the injection site occurs, photographs may be obtained. Detailed instructions for study drug administration are found in the Pharmacy Manual.

Dosing will be permitted at a location other than the study center (for example, the patient's home) by a healthcare professional with the oversight of the Investigator, provided the patient has tolerated at least 1 dose of study drug administered in the clinic. However, continued study

drug administration at the study center should be considered for patients who have ongoing study drug-related AEs or for anyone in the opinion of the Investigator who would benefit from clinical observation following dosing.

If a patient does not receive a dose of study drug within the specified visit window, the Investigator should contact the Medical Monitor. After such consultation, the dose may be administered or considered missed and not administered.

Additional details can be found in the Pharmacy Manual.

The definition of study drug overdose, follow-up procedures, and reporting requirements are provided Section 6.5.5.8.

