5.5. Study Drug Exposure and Compliance

The following variables will be summarized by descriptive statistics and/or frequency tabulation for the Safety Analysis Set:

- Duration of study drug exposure (months), defined as: (date of last exposure date of first dose +1)/30.44. Date of last exposure is the earliest date of the following:
 - date of last dose + 168 days (eg, the length of the longest dosing interval)
 - date of end of study
 - date of data cutoff for the analysis
- Cumulative study drug exposure time (patient-years)
- Number of patients on study drug for ≥ 1 day, ≥ 3 months, ≥ 6 months
- Number of doses received as continuous and categorical variables (1, 2, or 3)
- Cumulative number of doses received
- Number of missed doses (0, 1, 2, or 3) as a categorical variable
- Total study drug exposure (mg) as a continuous variable
- Total volume administered (mL)

5.6. **Prior and Concomitant Medications**

Medications will be coded using the World Health Organization (WHO) Drug Dictionary, version B3 WHO Drug Global - Sep 2018 or newer. Unique patients who reported medications will be summarized by Anatomical Therapeutic Chemical (ATC) level 3 class (or level 2 if not available) and PT. Summaries and listings for the Safety Analysis Set will be provided for prior and concomitant medications separately.

Prior medications are defined as medications with start date and stop date prior to the first dose of study drug. Concomitant medications are medications, other than the study drug, administered on or after the first dose date of study drug, as well as medications that started prior to the first dose of study drug and are ongoing after the first dose of study drug. If medication start date is on or after the date of first dose of study drug, the medication will be summarized as a concomitant medication even if the medication end date is missing. If the end date of a medication is missing or incomplete such that it cannot be determined whether it is after the first dose of study drug, it will be counted as a concomitant medication.

For missing or partial dates for medications, the imputation of start and end dates is described in Section 7.3.

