5.7.3.1. Kidney Stone Events

CT scans for radiographic kidney stone events are read in pairs blinded to visit date (baseline and Month 15). All kidney stone-related analyses in this section will be done with all data collected.

A clinical kidney stone event is defined as one of the following:

- Visible passage of a kidney stone
- A procedural intervention for removal of an asymptomatic or symptomatic stone (information on the location, number, and size of stones removed will be collected)
- Or, in the case of potential stone passages without visible stones, it will be up to the Investigator to evaluate patients' symptoms and determine whether a stone passage occurred or the symptoms were due to a different cause.

A radiographic kidney stone event is defined as a kidney stone that is increased in size by $\geq 2 \text{ mm}$ in at least one dimension or a new stone ($\geq 1 \text{ mm}$ in size) observed on CT at Month 15 relative to baseline.

Time to first kidney stone event

Time to first event is defined as date of the first study drug to the first date of a kidney stone event. Censoring applies to patients who do not have a kidney stone event during the study. The follow-up time of these patients will be censored at the lost to follow-up date, study discontinuation, data cut-off date, or end of study, whichever occurs first.

Time to the first kidney stone event will be analyzed for a combination of both clinical and radiographic kidney stone events and for clinical kidney stone events separately for both the 6-month primary analysis period and the 15-month DB period (FA). All available data at the time of each database lock will be used. Kaplan-Meier estimator will be used to estimate the distribution of time to first kidney stone event in each treatment group. A log-rank test will be used to evaluate the treatment differences between each dose and the placebo. In addition, Cox proportional hazard regression will be performed to estimate the hazard ratio along with the 95% CI and p-value for each dose compared to the placebo. The model includes treatment, number of historical kidney stone events (>1 versus \leq 1) in the 12 months prior to screening.

Incidence rate of clinical and radiological kidney stone events

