The incidence rate of kidney stone events will be analyzed for a combination of both clinical and radiographic kidney stone events and for clinical kidney stone events separately for both the 6-month primary analysis period and the 15-month DB period (FA).

The incidence rate will be calculated as the total number of kidney stone events divided by total person-years at risk during the respective period (ie, 6-month primary analysis period and 15-month DB period). Years at risk is defined as (time from first lumasiran dose until 168 days after the last dose of lumasiran, lost to follow-up date, study discontinuation, data cut-off date, or end of study, whichever occurs first)/365.25.

The endpoint will be analyzed using a negative binomial regression model that include fixed effects of the treatment arm and the number of historical kidney stone events (>1 versus \leq 1) in the 12 months prior to screening. The logarithm of the follow-up time of each patient will be included in the model as an offset variable. The p value and the ratio of mean kidney stone event rate between two treatment arms with the corresponding 95% CI will be estimated.

The total number of patients with at least one kidney stone event, total number of kidney stone events, total number of person-years will be presented. Descriptive statistics for the median and interquartile range of the kidney stone event rate will also be presented by treatment arm.

Other radiographic assessments

Change from baseline in radiographic assessments of kidney stones (eg stone volume) will be summarized descriptively.

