5.11.1. Adverse Events

Adverse events (AEs) will be classified by the MedDRA coding system (version 24.1) and displayed in tables and data listings using SOC and PT.

Treatment-emergent AEs (TEAEs) will be summarized, where TEAE is defined as any AE occurring or worsening on or after the first dose of study drug and through 168 days after the last dose or any study drug-related AE. Because any worsening AE is reported as a new AE with higher severity, programmatical comparison of severity is not needed for the classification of TEAE. For missing or partial dates for AEs, the imputation of start and end date can be found in Section 7.3. Events with a fully or partially missing onset date will be assumed to be treatment emergent unless it can be unequivocally determined (from the partial onset date and/or a partial or complete stop date) that the event occurred prior to the first dose of study drug. All TEAEs hereafter will be referred to as AEs in this document.

AEs will be summarized by the numbers and percentages of patients reporting a given AE. An overall table of TEAEs will include, but not limited to:

- At least 1 AE
- At least 1 drug related AE
- At least 1 severe AE
- At least 1 drug related severe AE
- At least 1 Serious Adverse Event (SAE)
- At least 1 drug related SAE
- At least 1 AE leading to treatment discontinuation
- At least 1 AE leading to drug interruption
- At least 1 drug related AE leading to treatment discontinuation
- At least 1 AE leading to study withdrawal
- At least 1 drug related AE leading to study withdrawal
- Death (based on SAE CRFs)

Tabulations by SOC and PT will be produced for the following:

- AEs,
- Treatment-related AEs,
- AEs by maximum severity,
- Treatment-related AEs by maximum severity,
- Severe AEs,
- Treatment-emergent SAEs,
- AEs leading to treatment discontinuation.

Tabulations by PT in decreasing order in frequency within each treatment arm will be produced for the following:

- AEs
- Treatment-related AEs
- SAEs

AEs and AEs related to treatment will also be summarized by severity. A patient contributes only once to the count for a given AE (overall, by SOC, by preferred term). Patients who report multiple occurrences of the same AE (preferred term) will be classified according to the most severe occurrence. An AE with missing severity will be assumed to be severe. An AE with missing study drug relatedness will be assumed to be related.

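### The kidney stone incidence rate counts every event in the period but stops person-time 168 days after the last dose, and the model offset is not tied to either window (minor, exploratory endpoint)

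*SAP*

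**What the plan says.** The incidence rate of kidney stone events is an exploratory endpoint (SAP 2.2.2.3), analysed in SAP 5.7.3.1 for the 6-month primary analysis period and the 15-month double-blind period.

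- **Rate:** "The incidence rate will be calculated as the total number of kidney stone events divided by total person-years at risk during the respective period".
- **Person-time:** "Years at risk is defined as (time from first lumasiran dose until 168 days after the last dose of lumasiran", or until loss to follow-up, leaving the study, the data cut or study end if one of these comes earlier.
- **Model:** negative binomial regression giving a rate ratio, 95% CI and p-value. "The logarithm of the follow-up time of each patient will be included in the model as an offset variable".
- **Follow-up time elsewhere in 5.7.3.1:** the time-to-first-event paragraph says of event-free patients: "The follow-up time of these patients will be censored at the lost to follow-up date, study discontinuation, data cut-off date, or end of study". It has no 168-day limit.
- **Data used:** 5.7.3.1 opens by saying that the stone analyses draw on all the data collected.

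For adverse events, SAP 5.11.1 does put the 168-day limit on the events: "any AE occurring or worsening on or after the first dose of study drug and through 168 days after the last dose". It then also admits any later event judged related to study drug.

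**The concern.** A rate needs its events and its person-time to come from the same window. Here the person-time has a 168-day limit after the last dose and the events do not. The period named in the rate sentence is the 6- or 15-month period, so it does not supply the missing limit. Read literally, an event after the limit enters the numerator while the days in which it arose are left out of the denominator, and the rate is too high.

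The offset adds a second uncertainty. If it is the truncated time, the mismatch carries into the rate ratio. If it runs to the end of observation, the model is sound but does not match the tabulated rate beside it. Two programmers could reasonably build it differently.

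A smaller matter is that years at risk start at the first dose of lumasiran, which placebo patients never receive. Study drug is evidently meant.

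The documents foresee the patients affected. Protocol 5.2.2 says of a dose outside its window: "After such consultation, the dose may be administered or considered missed and not administered", without requiring study exit. SAP 5.5 plans a table of "Number of missed doses (0, 1, 2, or 3) as a categorical variable". Under Protocol 4.3.1, patients who stop drug in the first six months are encouraged to "complete all assessments (including 24-hour urine collections) through Month 6, with early termination (ET) assessments at Month 9".

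**Working it through.** **Inputs.** Protocol Table 1: Month 3 dose Day 85 (±14), Month 6 visit Day 169 (±14), Month 9 dose Day 253 (±28), Month 15 visit Day 421 (±28). SAP 5.5 describes 168 days as the longest dosing interval.

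**The plan's own figure.** 253 − 85 = 168 and 421 − 253 = 168, so the 168 days reproduce.

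**Method.** Observed days = last observed day − 1. Days counted = min(last dose day + 168, last observed day) − 1. With a constant event rate and all events counted, the rate is inflated by observed ÷ counted.

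**15-month analysis, per patient**

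| Pattern | Limit (day) | Last observed day | Counted / observed days | Inflation |
|---|---|---|---|---|
| On-schedule completer | 253 + 168 = 421 | 421 | 420 / 420 | 1.00 |
| Completer at the window extremes (dose Day 225, visit Day 449) | 393 | 449 | 392 / 448 | 1.14 |
| Day 1 dose only, followed to Month 9 | 169 | 253 | 168 / 252 | 1.50 |
| Month 9 dose missed, followed to Month 15 | 253 | 421 | 252 / 420 | 1.67 |

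**Drift within the visit windows.** For a completer the days lost are max(0, X15 − X9), where X9 and X15 are the deviations from schedule. If these are assumed independent and uniform on whole days from −28 to 28, the mean loss is 9.5 days, or 9.5/420 = 2.3%, and the maximum is 56 days.

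**15-month analysis, arm level.** The documents give no expected share of affected patients, so an assumed share q is used. For a missed Month 9 dose with follow-up to Month 15, inflation is 420 ÷ [420(1 − q) + 252q]:

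- q = 5%: 1.020
- q = 10%: 1.042
- q = 20%: 1.087

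For a Day 1 dose only with follow-up to Month 9, and the rest on-schedule completers, inflation is [420(1 − q) + 252q] ÷ [420(1 − q) + 168q]. This gives 1.010, 1.021 and 1.045.

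**Rate ratio.** If q were 20% in one arm and 5% in the other, the crude ratio would shift by 1.087/1.020 = 1.065 (Month 9 missed) or 1.045/1.010 = 1.035 (Day 1 only). The modelled ratio would move in the same direction only if the offset is the truncated time.

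**6-month analysis.** With two in-window doses the earliest limit is (85 − 14) + 168 = Day 239 and the latest Month 6 visit is 169 + 14 = Day 183, so nothing is lost. A Day-1-only patient has a limit of Day 169 and loses at most 183 − 169 = 14 of 182 days (7.7%). With 20% such patients the arm's rate is at most 182 ÷ (182 − 14 × 0.20) = 1.016 times the correct one.

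**Radiographic events.** These are defined on the Month 15 CT. Under the same timing assumption, the Month 15 visit falls after the limit in (1 − 1/57)/2 = 49% of in-window completers. Simply dropping events after the limit would therefore discard many CT findings unless an assignment rule is given. CT is optional, so this applies only to patients who agree to it.

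**The case against.** The strongest reply is that this is loose wording rather than a wrong rule. By ordinary convention an incidence rate counts events that occur during the time at risk, and the offset sentence follows shortly after the definition of years at risk, so the same quantity may be meant. The time-to-event text concerns censoring of event-free patients in another analysis. The remark about using all collected data may only waive the medication exclusions applied to the urine endpoints. The adverse event definition is not a clean contrast, because it also admits later drug-related events. Table shells and specifications are in a separate document that was not available.

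The schedule also aligns many cases. Early stoppers are followed to about six months after the last dose, and a patient last dosed at Month 3 who has early termination at Month 9 ends on Day 253 = 85 + 168. The distortion is also small against sampling error. Forty patients for 420 days give 40 × 420/365.25 = 46 person-years. At an assumed 0.2 to 1.0 events per year that is about 9 to 46 events, with a standard error of roughly 33% to 15% on the log rate.

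Much of this stands as to size, and the adverse event comparison is only supporting evidence. It does not supply the missing limit on events. If the offset is read as years at risk, the two denominators agree but the truncated time enters the model against untruncated events.

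**Conclusion.** The concern holds and is minor. As written, the rate counts late events without their person-time and leaves the offset open.

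The tabulated 15-month rate is unaffected for on-schedule completers. It is about 2% too high from visit-window drift under the uniform-timing assumption, and about 2% to 9% too high if 5% to 20% of an arm miss Month 9 and stay. Those shares are assumptions, and a constant event rate is assumed throughout. The 6-month rate is at most 1.6% too high even with 20% Day-1-only patients.

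The rate ratio is biased only if the offset is the truncated time and these patterns differ by arm, which the documents give no particular reason to expect. The endpoint is exploratory, and the primary and secondary analyses do not depend on it.

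**What to change.** In SAP 5.7.3.1, define one window per patient, starting at the first dose of study drug in every arm, and use it for the event count, the person-years and the log offset. Say explicitly that the offset is the log of that time. Either version works:

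1. Run person-time to the end of observation within the analysis period and count all events in it.
2. Keep the 168-day on-treatment limit, count only events inside it, and state how a stone found on a Month 15 CT after the limit is assigned.

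Replace lumasiran with study drug in the years-at-risk definition.

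The cost is a wording change, since all the dates are already collected. It is best made before the analysis: SAP 2.5 leaves the sponsor unblinded throughout, so a later choice of window would be made with arm-level data in view.

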5.7.3.2. Pharmacodynamics

The PD exploratory endpoints are described in Section 5.8.

5.7.3.3. Change from Baseline in eGFR

Descriptive statistics of eGFR along with mean (+/-SEM) figures and individual spaghetti plots will be presented for the actual values, change from baseline, and percent change from baseline for each treatment arm by visit.

5.7.3.4. Healthcare Utilization and Quality of Life

Kidney stone event related hospitalizations, emergency room visits, unscheduled office visits, or procedures

Healthcare utilization associated with a kidney stone event will be descriptively summarized for the number of visit type (hospitalization, emergency room, urgent care center, unscheduled office visit, other) per patient, cumulative length of hospital stay (days), and cumulative length of stay in the ICU. The number of, and percent of, patients with different type of visits (hospitalization, emergency room, urgent care center, unscheduled office visit, other) will also be presented.

Patient-reported severity and symptomatic and functional impact of kidney stone events

Quality of life (QoL) outcomes will be summarized using a two-sample t-test for the difference between the mean scores of each lumasiran dose to the placebo. The analyses will be performed

using the worst scores post-baseline as reported by the patients and also using the scores from the most severe clinical kidney stone event as graded by the investigators (Refer to protocol Section 6.5.5.1 for definition of clinical kidney stone grade).

The QoL will also be summarized by treatment group for the actual values, change from baseline (Day 1), and percent change from baseline to the first clinical kidney stone event, to the most severe clinical kidney stone event as graded by the investigators, and to worst scores post-baseline as reported by the patients. Baseline for the Brief Pain Inventory-Short Form (BPI-Short Form) is defined as the mean score during Screening and Day 1 visits. This summary will be done excluding patients who have a kidney stone event during Screening/Day 1 as a sensitivity analysis.

For the QoL analyses, if a patient has multiple clinical kidney stones with the same grade, the first severe clinical kidney stone event will be used for the analysis.

5.7.4. Evaluation of Subgroups

Subgroup analyses will be conducted to assess the consistency of treatment effect within the various subgroups defined by the following baseline characteristics:

- Age $(18 \text{ to } < 65, \ge 65)$
- Sex (Male, Female)
- Race (White, Black, All others)
- BMI (kg/m^2) (<30; \geq 30)
- *AGXT* heterozygous (Yes/No)
- 24-hr urinary oxalate (≤ 1.25 ULN, > 1.25 ULN)
- Historical kidney stone events in the 12 months prior to screening $(\leq 1, >1)$

- Calcium oxalate stone composition ($\leq 75\%$, >75%)
- History of diabetes (Yes, No)

Subgroup analyses will be performed for the primary endpoint of percent change in 24-hour urinary oxalate to Month 6 using the FAS population. A forest plot will be generated to illustrate the estimated treatment effect along with the associated 95% CI. If the number of patients in a subgroup for either arm is less than 10 patients, then only descriptive statistics will be generated.

Other subgroups may be examined, if deemed appropriate. The subgroup analyses may also be performed for other efficacy endpoints.

5.8. Pharmacodynamic Analyses

The PD parameters include plasma oxalate, plasma glycolate, 24-hour urinary glycolate:creatinine ratios, and spot urinary oxalate:creatinine ratios. Summary tables, mean (+/-SEM) figures, and individual spaghetti plots will be provided for observed values, absolute changes, and percentage changes from baseline for each scheduled time point by treatment group. FAS is used for all PD parameters except for plasma oxalate where a separate analysis population, Plasma Oxalate Analysis Set is used.

The number and percent of patients with 24-hour urinary oxalate \leq ULN (40 mg) and the number and percent of patients having a 25% reduction in urinary calcium oxalate supersaturation will be presented over time.

